9.1.6. Case Report Forms

An eCRF casebook will be completed by an authorized study personnel member whose training for this function is completed in the electronic data capture (EDC) system unless otherwise directed. The eCRF casebook will only capture the data required per the protocol schedule of events and procedures, unless collected by a non-EDC vendor system (eg, central laboratory). The Inclusion/Exclusion Criteria and Enrollment eCRFs should be completed only after all data related to eligibility are available. Data entry should be performed in accordance with the CRF Completion Guidelines provided by the sponsor. Subsequent to data entry, a study monitor may perform source data verification. System-generated or manual queries will be issued in the EDC system as data discrepancies are identified by the study monitor or Gilead personnel who

routinely review the data for completeness, correctness, and consistency. The site investigator, site coordinator, or other designee is responsible for responding to the queries in a timely manner, within the system, either by confirming the data as correct or updating the original entry, and providing the reason for the update (eg, data entry error). Original entries as well as any changes to data fields will be stored in the audit trail of the system. Regular oversight by the principal investigator of the data entered into the EDC system is expected to occur on an ongoing basis throughout the study to ensure quality and completeness. At a minimum, before any interim, final, or other time points (as instructed by Gilead), the investigator will apply his/her electronic signature to confirm that the forms have been reviewed and that the entries accurately reflect the information in the source documents. At the conclusion of the study, Gilead will provide the site investigator with a read-only archive copy of the data entered. This archive must be stored in accordance with the records retention requirements outlined in Section [9.1.5](#).

9.1.7. Investigator Inspections

The investigator will make available all source documents and other records for this study to Gilead's appointed study monitors, to IRB/IEC, or to regulatory authority or health authority inspectors.

9.1.8. Protocol Compliance

The investigator is responsible for ensuring the study is conducted in accordance with the procedures and evaluations described in this protocol.

9.2. Sponsor Responsibilities

9.2.1. Protocol Modifications

Protocol modifications, except those intended to reduce immediate risk to study participant, may be made only by Gilead. The investigator must submit all protocol modifications to the IRB/IEC in accordance with local requirements and receive documented IRB/IEC approval before modifications can be implemented.

9.2.2. Study Reports and Publications

A clinical study report (CSR) will be prepared and provided to the regulatory agency(ies) when applicable and in accordance with local regulatory requirements. Gilead will ensure that the report meets the standards set out in the ICH Guideline for Structure and Content of Clinical Study Reports (ICH E3). Note that an abbreviated report may be prepared in certain cases. For studies with sites in countries following the EU Regulation No. 536/2014, a CSR will be submitted within 1 year (6 months for pediatric studies, in accordance with Regulation [EC] No. 1901/2006) after the global end of study (as defined in Section [3.4.2](#)).

Investigators in this study may communicate, orally present, or publish study data in scientific journals or other scholarly media in accordance with the Gilead clinical trial agreement.

9.3. Joint Investigator/Sponsor Responsibilities

9.3.1. Regulatory and Ethical Consideration

This study will be conducted in accordance with the protocol and the following:

- The ethical principles of the Declaration of Helsinki
- ICH Good Clinical Practice (GCP)
- Applicable laws and regulatory requirements, including Regulation [EU] No 536/2014 (Regulation [EU] no 536/2014 Annex I, Section D, No. 17, letter a).

9.3.2. Payment Reporting

Investigators and their study personnel may be asked to provide services performed under this protocol (eg, attendance at investigator meetings). If required under the applicable statutory and regulatory requirements, Gilead will capture and disclose to federal and state agencies any expenses paid or reimbursed for such services, including any clinical study payments, meal and/or travel expenses or reimbursements, consulting fees, and any other transfer of value.

9.3.3. Access to Information for Monitoring

In accordance with regulations and guidelines, the study monitor must have direct access to the investigator's source documentation and any participant records in order to verify the adherence to the protocol and the accuracy of the data recorded in the eCRF. The study monitor is responsible for routine review of the case report form/eCRF at regular intervals throughout the study to verify adherence to the protocol and the completeness, consistency, and accuracy of the data being entered on them. The investigator agrees to cooperate with the study monitor to ensure that any problems detected through any type of monitoring (central, off-site, on-site) are resolved.

9.3.4. Access to Information for Auditing or Inspections

Representatives of regulatory authorities or Gilead may conduct inspections or audits of the clinical study. If the investigator is notified of an inspection by a regulatory authority, the investigator agrees to notify the Gilead study monitor immediately. The investigator agrees to provide to representatives of a regulatory agency or Gilead access to records, facilities, and personnel for the effective conduct of any inspection or audit.

9.3.5. Study Discontinuation

Gilead reserves the right to terminate the study at any time, and the investigator has the right to terminate the study at his or her site. Should this be necessary, both parties will arrange discontinuation procedures and notify the participants, appropriate regulatory authority(ies), and IRB/IEC. In terminating the study, Gilead and the investigator will ensure that adequate consideration is given to the protection of the participant's interests.

11.2. Committees

11.2.1. Safety Review Team

An SRT will make dose selection decision for future cohorts based on data described in Section 1.4.

An SRT charter defining the team membership, meeting conduct, and decision-making process will be agreed upon by all team members before the first participant is dosed for cohorts required dose selection. The data reviewed at the team meeting to make dose selection decisions will be defined in the charter. The quality control checks performed on the data reviewed and used for making dose selection will also be described in the charter.

Source data verification may not be performed before SRT meetings. Alternative data quality control checks that are performed on data used to make selection decisions are described in the SRT charter (or similar document).

11.2.2. Data Monitoring Committee

A multidisciplinary DMC consisting of non-Gilead personnel will review the progress of the study, perform interim reviews of safety and PK (if available) data, and provide recommendation to Gilead whether the nature, frequency, and severity of AEs associated with study treatment warrant the early termination of the study in the best interests of the participant, whether the study should continue as planned, or whether the study should continue with modifications. The DMC may also provide recommendations as needed regarding study design.

The DMC's specific activities will be defined by a mutually agreed charter, which will define the DMC's membership, conduct, and meeting schedule.

While the DMC will be asked to advise Gilead regarding future conduct of the study, including possible early study termination, Gilead retains final decision-making authority on all aspects of the study.

11.3. Pandemic Risk Assessment and Mitigation Plan

During an ongoing pandemic, potential risks associated with participants being unable to attend study visits have been identified for this study.

These risks can be summarized as follows:

- 1) Study drug supplies to participants and sites:
 - a. Participants may be unable to return to the site for a number of visits to get the study drug, or the site may be unable to accept any participant visits. Without study drugs, the participant would not be able to continue receiving the study drug as planned per protocol.

Mitigation plan: Study drug supplies may be provided to the participant from the site without a clinic visit, once it is confirmed that the participant may safely continue on study drug as determined by the principal investigator. A remote study visit, via phone, or videoconferencing, must be performed before remote study drug resupply. At the earliest opportunity, the site will schedule in-person participant visits and return to the protocol's regular schedule of assessments. A qualified courier may be utilized to ship the study drug from sites to study participant if permitted by the local ethics committee/IRB/regulatory authority as applicable and with sponsor's approval.
 - b. Shipments of study drug could be delayed because of transportation issues. Without study drug, the participant would not be able to continue receiving the study drug as planned per protocol.

Mitigation plan: The site's study drug inventory should be closely monitored. Site staff should notify the sponsor or delegate if they foresee shortage in study drug inventory or if there is any interruption in local shipping service. The sponsor will continue to monitor inventory at the study drug depot and investigational sites. Manual shipments will be triggered as necessary.
- 2) Participant safety monitoring and follow-up:
 - a. Participant may be unable or unwilling to come to the investigational site for their scheduled study visits as required per protocol.

Mitigation plan: For participant who may be unable or unwilling to visit the investigational site for their scheduled study visits as required per protocol, the principal investigator or qualified delegate will conduct a remote study visit, via phone, or videoconferencing, to assess the participant within the target visit window date whenever possible. During the remote study visit, the following information at minimum will be reviewed:

- i. Confirm if participant has experienced any AEs/SAEs/special situations (including pregnancy) and follow up on any unresolved AEs/SAEs.
 - ii. Review the current list of concomitant medications and document any new concomitant medications.
 - iii. If applicable, confirm electronic diary questionnaires and participant-reported outcomes have been completed and transmitted.
 - iv. If applicable, confirm the participant's study drug supply is sufficient to last until the next planned visit date. If study drug resupply is needed, it will be provided as described above in (1).
 - v. If applicable, remind the participant to maintain current dosing and to keep all dispensed study drug kits for return at the next on-site visit.
- b. Participant may be unable or unwilling to travel to the site for planned assessments (eg, safety blood draws); hence samples may not be sent for central laboratory analyses.
- Mitigation plan: Local laboratories or other vendors may be utilized as appropriate to monitor participant safety until the participant can return to the site for their regular follow-up per protocol. Any changes in the party conducting laboratory assessments for the study because of the pandemic will be documented accordingly. Pregnancy testing may be performed using a home urine pregnancy test if local laboratory pregnancy testing is not feasible.
- 6) Participant may be unable or unwilling to attend the study visit to sign an updated ICF version.

Mitigation plan: The site staff will follow their approved consent process and remain in compliance with the local ethics committee/IRB and national laws and regulations. Remote consent will be allowed if has been approved by the local ethics committee/IRB. The consent process will be documented and confirmed by normal consent procedure at the earliest opportunity.

- 3) Protocol and monitoring compliance:
- 7) Protocol deviations may occur in case scheduled visits cannot be conducted as planned per protocol.

Mitigation plan: If it is not possible to complete a required procedure, an unscheduled visit should be conducted as soon as possible when conditions allow. The situation should be recorded and explained as a protocol deviation. Any missed participant visits or deviation to the protocol because of the pandemic must be reported in the eCRF and described in the CSR. Any remote study visits that are conducted in lieu of clinic visits because of the pandemic will be documented as a protocol deviation related to the pandemic.

- a. Study monitors may be unable to carry out source data review or source data verification, or study drug accountability or assess protocol and GCP compliance. This may lead to delays in source data verification, an increase in protocol deviations, or underreporting of AEs.

Mitigation plan: The study monitor is to remain in close communication with the site to ensure data entry and query resolution. Remote source data verification may be arranged if allowed by local regulation and the Study Monitoring Plan. The study monitor is to reference the Study Monitoring Plan for guidance on how to conduct an off-site monitoring visit. The study staff is to save and document all relevant communication in the study files. The status of sites that cannot accept monitoring visits and/or participant on site, must be tracked centrally and updated on a regular basis.

4) Missing data and data integrity:

- a) There may be an increased amount of missing data because of participant missing visits/assessments. This could have an impact on the analysis and the interpretation of clinical study data.
- b) Mitigation plan: Implications of a pandemic on methodological aspects for the study will be thoroughly assessed and documented, and relevant actions will be taken as appropriate (eg, modification of the SAP) and in compliance with regulatory authorities' guidance. Overall, the CSR will describe the impact of the pandemic on the interpretability of study data.

Risks will be assessed continuously, and temporary measures will be implemented to mitigate these risks as part of a mitigation plan, as described above. These measures will be communicated to the relevant stakeholders as appropriate and are intended to provide alternate methods that will ensure the evaluation and assessment of the safety of participant who are enrolled in this study.

Since these potential risks are considered mitigated with the implementation of these measures, the expected benefit-risk assessment of ODV in study participant remains unchanged.

11.4. Pregnancy Precautions, Definition of Childbearing Potential, and Contraceptive Requirements

1) Definitions

a) Definition of Childbearing Potential

For the purposes of this study, a participant assigned female at birth is considered of childbearing potential following the initiation of puberty (Tanner stage 2, Tanner staging only required if the participant is believed to be prepubescent) until becoming postmenopausal, or unless the participant is permanently sterile or has medically documented ovarian failure. Permanent sterilization includes hysterectomy, bilateral oophorectomy, or bilateral salpingectomy in a participant assigned female at birth of any age.

Participants assigned female at birth are considered to be in a postmenopausal state when they are at least 54 years of age with cessation of previously occurring menses for at least 12 months without an alternative cause. In addition, participants assigned female at birth younger than 54 years with amenorrhea of at least 12 months also may be considered postmenopausal if their follicle-stimulating hormone level is in the postmenopausal range and they are not using hormonal contraception or hormonal replacement therapy.

b) Definition of Fertility in a Participant Assigned Male at Birth

For the purposes of this study, a participant assigned male at birth is considered fertile after the initiation of puberty unless the participant is permanently sterile by bilateral orchidectomy or with medical documentation.

2) Contraception Requirements for Participants Assigned Female at Birth and of Childbearing Potential

a) Study Drug Effects on Pregnancy and Hormonal Contraception

Obeldesivir is contraindicated in pregnancy as a malformative effect is noted in early pregnancy based on nonclinical data. An increased rate of adverse fetal effects, including postimplantation loss and fetal visceral malformations related to the development of the heart, blood vessels, and liver, were noted in rabbits administered ODV CCI [REDACTED] Data from clinical pharmacokinetic interaction studies of ODV have demonstrated that there is no reduction in the clinical efficacy of hormonal contraception. Refer to the latest version of the investigator's brochure for additional information.

b) Contraception Requirements for Participants Assigned Female at Birth and of Childbearing Potential

The inclusion of participants assigned female at birth and of childbearing potential requires the use of highly effective contraceptive measures with a failure rate of less than 1% per year. They must have a negative pregnancy test at the screening visit before randomization. A pregnancy test will also be performed at the EOS visit.

Duration of required contraception for participants assigned female at birth and of childbearing potential in this clinical study should start from the screening visit until 14 days after the last study dose.

Participants assigned female at birth and of childbearing potential must agree to 1 of the following contraceptive methods:

Complete abstinence from intercourse of reproductive potential. Abstinence is an acceptable method of contraception only when it is in line with the participant's preferred and usual lifestyle.

Or

Consistent and correct use of 1 of the following methods of birth control listed below:

- Nonhormonal intrauterine device
- Bilateral tubal occlusion (upon medical assessment of surgical success)
- Vasectomy in the partner assigned male at birth (upon medical assessment of surgical success)

Or

Participants assigned female at birth and of childbearing potential who wish to use a hormonally based method must use it in conjunction with a barrier method, preferably a male condom. Hormonal methods are restricted to those associated with the inhibition of ovulation. Hormonally based contraceptives and barrier methods permitted for use in this protocol are as follows:

- Hormonal methods (each method must be used with a barrier method, preferably male condom)
 - Oral contraceptives (either combined or progesterone only)
 - Injectable progesterone
 - Transdermal contraceptive patch
 - Contraceptive vaginal ring
- Barrier methods (each method must be used with a hormonal method)
 - Male condom (with or without spermicide)
 - Female condom (with or without spermicide)
 - Diaphragm with spermicide
 - Cervical cap with spermicide

— Sponge with spermicide

Inclusion of methods of contraception in this list of permitted methods does not imply that the method is approved in any country or region. Methods should only be used if locally approved.

Participants assigned female at birth and of childbearing potential must also refrain from egg donation and in vitro fertilization during treatment and until the end of contraception requirement.

The above requirements apply only as specified, and not to sexual encounters in which pregnancy is not a possible outcome.

3) Contraception Requirements for Participants Assigned Male at Birth

It is theoretically possible that a relevant systemic concentration of study drug may be achieved in a partner assigned female at birth from exposure to the participant's seminal fluid and pose a potential risk to an embryo/fetus. A participant assigned male at birth with a partner assigned female at birth and of childbearing potential must use highly effective contraceptive measures with a failure rate of less than 1% per year through at least 14 days after last dose of study drug. Please refer to the contraceptive requirements listed above for female participants.

Participants assigned male at birth must also refrain from sperm donation or cryopreservation of germ cells during treatment and until the end of contraception requirement.

The above requirements apply only as specified, and not to sexual encounters in which pregnancy is not a possible outcome.

4) Unacceptable Birth Control Methods

Birth control methods that are unacceptable include periodic abstinence (eg, calendar, ovulation, symptothermal, postovulation methods), withdrawal (coitus interruptus), spermicides only, and lactational amenorrhea method. A female condom and a male condom should not be used together.

5) Procedures to Be Followed in the Event of Pregnancy

Participants assigned female at birth will be instructed to notify the investigator if they become pregnant or suspect they are pregnant at any time from start of the study to 30 days after the last study drug dose. Study drug must be discontinued immediately, and medical monitor should be notified.

Participants assigned male at birth whose partner has become pregnant or suspects they are pregnant from start of study to 30 days after the last study drug dose must also report the information to the investigator. Instructions for reporting pregnancy, partner pregnancy, and pregnancy outcome are outlined in Section [7.4.2.3](#).

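### Appendix 11.4 item 3 rests the male rule on embryo/fetal risk from semen but sets no visible measure for an already pregnant partner, and Section 7.4.2.3 is narrower than item 5 on partner pregnancies

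*Protocol*

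**What the plan says.** **Hazard.** Appendix 11.4, item 2a, states: "Obeldesivir is contraindicated in pregnancy as a malformative effect is noted in early pregnancy based on nonclinical data". It describes postimplantation loss and visceral malformations in rabbits; the dose is redacted.

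**Male rule.** Item 3 opens: "It is theoretically possible that a relevant systemic concentration of study drug may be achieved in a partner assigned female at birth", and names as the source the participant's "seminal fluid and pose a potential risk to an embryo/fetus". A male participant whose partner is of childbearing potential must then use highly effective contraception "through at least 14 days after last dose of study drug". For methods, item 3 refers back to the list for female participants. The item closes with the exemption "The above requirements apply only as specified, and not to sexual encounters in which pregnancy is not a possible outcome". The same sentence also closes the requirements for female participants; the occurrence that matters here is the one that ends item 3.

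**Notification.** Item 5 has a male participant "whose partner has become pregnant or suspects they are pregnant from start of study to 30 days after the last study drug dose" tell the investigator. It then adds: "Instructions for reporting pregnancy, partner pregnancy, and pregnancy outcome are outlined in Section" 7.4.2.3.

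**Reporting to the sponsor.** The opening sentence of Section 7.4.2.3 has the investigator report participants' pregnancies up to 30 days after the last dose. For partners, it covers pregnancies that result from exposure to a participant's sperm while contraception is required. A second sentence gives a 24-hour deadline and a form for pregnancies in general. A later sentence asks for the outcome of participant and partner pregnancies alike.

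**The concern.** Item 3 names an exposure route and a victim: drug in semen, and an embryo or fetus. The one situation in which an embryo or fetus is certainly present is a partner who is already pregnant, and item 3 does not mention her. A site that followed the wording literally would give a participant with a pregnant partner no precaution, although the same appendix contraindicates the drug in pregnancy.

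The second issue is how two linked steps fit together. The participant tells the investigator under item 5, and the investigator tells the sponsor under 7.4.2.3. If the second step covers fewer pregnancies than the first, some are notified and then left to the site's judgement. A pregnancy already under way during dosing is among these, and it is the kind that bears most directly on the hazard item 3 describes.

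**Working it through.** No sample size, power or error rate is involved. The check compares the texts, with simple arithmetic on the days.

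**1. Does the male rule reach an already pregnant partner?** Item 1a defines childbearing potential for participants only, so both ways of applying it to a partner need checking.
- If the definition carries over, pregnancy does not end the status, since it runs from puberty to menopause or sterility. The duty in item 3 then reaches her, but another conception is not a possible outcome, so the closing exemption read literally releases the encounter.
- If it does not carry over, the duty in item 3 has no clear application to her.

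Either way, the visible text yields no clear measure.

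**2. Would the permitted methods protect her anyway?** The list that item 3 borrows accepts a nonhormonal intrauterine device or tubal occlusion alone. Neither keeps semen from the partner. Only a condom or abstinence addresses the stated route, and neither is required specifically for a pregnant partner.

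**3. Could the measure stand elsewhere?** No pregnancy or contraception criterion is visible in Sections 4.2 and 4.3. Exclusion criteria 4 and 6 to 10 are redacted and could contain one.

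**4. Item 5 against 7.4.2.3.**

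| | Item 5 | 7.4.2.3, opening sentence |
|---|---|---|
| Who reports to whom | Participant to investigator | Investigator to sponsor |
| Which partner pregnancies | Partner has become, or suspects being, pregnant | Those resulting from participant sperm exposure |
| Period | Start of study to 30 days after last dose | While contraception is needed |

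With the last dose on Day 5, the contraception period ends no earlier than 5 + 14 = Day 19, and item 5 ends at 5 + 30 = Day 35. For female participants the contraception period "should start from the screening visit until 14 days after the last study dose"; for male participants item 3 states no start. A pregnancy conceived before the contraception period but first suspected on study falls under item 5 and outside the opening sentence of 7.4.2.3.

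**5. Text that softens the mismatch.** The 24-hour sentence in 7.4.2.3 has no limit of its own on cause or conception date, but it follows directly on the scope sentence and can be read as the timing for those pregnancies. The outcome sentence includes partner pregnancies without limit, but concerns outcome rather than the initial report. Sections 7.1.3 and 7.3.4 make pregnancy a special situation reportable from study drug initiation onwards, without naming partners.

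**6. Is 14 days long enough for the added precaution?** Section 1.2.1.2.1 gives a median GS-441524 plasma half-life of 6 to 7 hours. Fourteen days are 14 × 24 = 336 hours; 336/7 = 48 and 336/6 = 56 half-lives. The period can stay as it is.

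**The case against.** The strongest reply is that item 3 is a conception-prevention rule, consistently applied: it stands under a contraception heading, borrows a contraceptive list and ends with a stock exemption. On that view a condom rule for pregnant partners is an extra precaution against a route that the protocol calls only theoretical. This explains how the text arose. It does not answer the reason item 3 itself gives, which is risk to an embryo or fetus from exposure rather than conception as such.

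Four stronger readings are tempting, and the documents do not support them.
- *The plan leaves pregnant partners unprotected.* A reader might infer this, but the redacted criteria may hold the measure. Only the visible text can be faulted.
- *The investigator has no instruction for a partner pregnancy.* This goes too far. Section 7.4.2.3 supplies a form, a recipient and a 24-hour deadline, and item 5 names it for partner pregnancy. What is unclear is scope.
- *The 30-day and 14-day periods contradict each other.* One governs notification to the investigator; the other limits the sperm exposure that led to conception. They belong to two linked steps, so the difference between them does not measure a gap.
- *A sizeable share of partner pregnancies would go unreported.* The documents give neither a pregnancy rate nor a time from conception to recognition, so no share can be stated.

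One further point stands in part. The window in item 5 can be read as dating when the partner became pregnant, so that a pregnancy known before the study need not be notified at all. The mismatch then shrinks mainly to earlier conceptions first suspected on study, but it does not vanish.

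**Conclusion.** Both parts hold on the visible text, at minor weight. Item 3 states a concern about embryo/fetal exposure and, read literally, sets no measure for a partner who is already pregnant. The opening sentence of 7.4.2.3 is narrower than the item that sends the reader there, and the softening sentences do not clearly widen it.

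The number of participants affected is very small. The point concerns pubertal male participants with a pregnant partner, mainly in Cohort 1 (12 evaluable participants), over dosing and at least the following 14 days. That the expected number of cases is well below one is an assumption; the documents give no figure. The malformation signal is nonclinical. No endpoint, analysis set or dose decision depends on this, and it is no reason to hold the trial. The first part falls away if a redacted criterion already contains the measure.

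**What to change.** In Appendix 11.4, item 3, add after the closing exemption: *This exemption does not apply when the partner is pregnant. In that case the participant must use a male condom or abstain from intercourse during dosing and for at least 14 days after the last dose.* If a redacted criterion already says so, a cross-reference to it is enough.

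In Section 7.4.2.3, replace the partner clause with: *and any partner pregnancy notified to the investigator under Appendix 11.4, item 5, from start of study to 30 days after the last dose, including one already under way during dosing.*

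The cost is two sentences and one clause. Protocol amendments are already foreseen for the younger cohorts, and no visit or test is added. The downside is a few extra reports about people who are not participants, and a counselling point that can be sensitive with pubertal male participants.
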